Subjects: In a second study, we investigated the effects of an isocaloric high protein diet in non-diabetic obese subjects. In order to determine the effects of isocaloric increased protein meal replacements, 100 obese volunteers were recruited to participate in a 3-month study of meal replacements with either 0.5 g/lb lean body mass/day or 1.0 g/lb lean body mass/day. There were a total of 75 females (41 in group A and 34 in group B) and 25 males (9 in group A and 16 in group B) in the preliminary study. The meal replacements were isocaloric with carbohydrate substituted for protein and dietary fat held constant at 20%. Sixty percent of the subjects have completed the study. The 86 subjects who finished the study are included in this analysis. Mean baseline BMI was 33.63 kg/m^2 (range 27 to 43); mean baseline age was 49.7 years (range 24 to 71). Participants were randomized to either the HP MR treatment group ($n=42$) or standard protein (SP) MR group ($n=46$). Both groups received dietary counseling at baseline, as well as at 2, 4, 8, and 12 weeks. 12-week follow-up data were available in 86 subjects (42 HP, 44 SP). At 12 weeks, the HP and SP groups both lost significant amounts of weight (males: 235.96 ± 7.28 to 221.73 ± 9.34 lbs in HP, 231.5 ± 8.09 to 217.69 ± 7.73 lbs in SP; females: 198.66 ± 4.68 to 188.98 ± 4.53 lbs in HP, 194.19 ± 4.58 to 182.34 ± 5.33 lbs in SP). In the HP versus the SP group, there were no statistically significant differences in changes in weight (-11.1 vs. -11.9 lbs; $p=0.80$), waist circumference (-3.9 vs. -3.0 cm; $p=0.34$), hip circumference (-2.0 vs. -1.08 cm; $p=0.94$), bioelectrical impedance analysis (BIA) fat mass (-7.4 vs. -4.3 lbs; $p=0.17$), total cholesterol (-17.5 vs. -6.3 mg/dL), LDL cholesterol (-11.3 vs. -8.3; $p=0.77$), and HDL cholesterol (+1.3 vs. +0.5 mg/dL; $p=0.62$). A statistically significant reduction in the HP group was observed with regard to fat mass (-1.82 ± 0.66 lbs for HP and 0.24 ± 0.68 for SP, $p=0.0395$) as shown in Fig. 2 and triglyceride concentration (-42.5 vs. -0.3 mg/dL). This analysis demonstrates the potential of increased protein supplementation to result in retention of lean body mass at equivalent weight losses, but longer-term studies are needed to expand on these findings.

C. Alteration of Ghrelin Plasma Levels in Patients' with Neuroendocrine Tumors:

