Insulin/Glucose: Insulin is measured using a commercial double antibody 1^{125} method. Glucose is measured using spectrophotometry at 505 nm absorbance.

Lipids — Cholesterol, High Density Lipoprotein (HDL) Cholesterol, Triglycerides: Plasma cholesterol and triacylglycerol are determined using standard enzymatic methods. The interassay coefficients of variation are less than 4% and interassay variation is usually less than 2%. These levels of precision are required for the types of nutritional studies carried out by the core in recent years demonstrating statistically significant changes in total cholesterol with adherence to a low fat diet and modest weight loss. Concentrations of alpha cholesterol are determined enzymatically. The alpha cholesterol is derived from the measurement on the supernatant following the precipitation of apo B containing lipoproteins with Heparin and MnCl₂. The so-called low density lipoprotein (LDL) or beta lipoprotein cholesterol is estimated from these data using the Friedenwald equation. For seven years, the laboratory has participated with the Centers for Disease Control in the standardization program for measuring cholesterol, HDL cholesterol and triacylglycerol and it continues to meet the criteria required by the center for disease control in the analyses of these plasma lipids. The laboratory has been assigned a Laboratory I.D. No. LSP 266 for the ODC-NHLB1 Lipid Standardization Program.

viii. Hormonal and Biochemical Assays: The ability to conveniently and rapidly profile a diverse set of peptides has valuable applications. The comparison of a biomarker profile is important both for the better understanding of pathophysiology and for the development of improved clinical diagnostics. In a step toward further enabling such a capability, we propose to utilize a biomarker kit based on Phoenix Pharmaceuticals. This kit is able to measure levels of GLP-1, PYY₃₋₃₆, adiponectin, IGF-1, interleukin (IL)-6, leptin, acyl ghrelin, CCK, gastrin and tumor necrosis factor (TNF)-alpha. We intend to measure leptin, IGF-1, TNF-alpha, and IL-6 concentrations because recent studies have demonstrated a strong positive correlation of serum levels with percentage of body fat.

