Data Analysis: Descriptive statistics (mean, standard deviation, median, inter-quartile range, and frequency distribution) of demographic information and baseline assessments will be generated to characterize the study participants. Patient characteristics and baseline measurements of the three diet groups will be compared using analysis of variance (ANOVA) for continuous variables, and Chi-square test for categorical variables to evaluate the appropriateness of the randomization. If the distribution of the variable is skewed, an appropriate variable transformation will be made before the comparison. Nonparametric methods, such as Kruskal-Wallis one-way analysis of variance, will also be used for comparison.

Primary Endpoint: the primary endpoint is change in body weight, which is calculated as the difference between Day 1 (baseline) and 16 weeks. The primary objective is to compare the weight loss between the high-protein diet and the standard diet. We will use ANOVA to compare the change in weight among the three groups (through contrast), and also use ANCOVA to compare the weight loss among these groups, adjusting for the baseline values and gender. If the primary endpoint is non-normally distributed, the Kruskal-Wallis one-way analysis of variance will be used.

Secondary Endpoints: The secondary endpoints are (1) efficacy variables: nutrition assessments (FFQ, 3DFR, and satiation questionnaire), anthropometric profiles (e.g., waist and hip circumferences), laboratory and biochemical variables (e.g., insulin, lipid levels, HbA1c), body composition (e.g., body fat), liver stiffness, microbiome changes, and level of hormones; (2) safety variables: incidence, severity and duration of adverse events, vital signs, concomitant medications and physical examination results.

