Shotgun reads will be inputted into HUMAnN2 for annotation of gene families and identification of the microbial source of these genes⁽⁷⁶⁾. Individual genes will be aggregated into functional pathways using the MetaCyc database⁽⁷⁷⁾. Gene and pathway abundance for the HPD and NPD groups at baseline will be compared to confirm that randomization prevented skewing of the functional profiles of the two groups. Pathway abundance will be fitted to a multivariate model using DESeq2 with diet group/time point, baseline BMI, age, sex, and smoking status as covariates to identify functional pathways impacted by a high protein diet after adjusting for covariates. Genes belonging to HPD-associated pathways, stratified by the genus of their microbial source, will then be individually evaluated using DESeq2. This approach will reduce the number of statistical tests which might be overwhelming given the greater than 5 million genes within the intestinal metagenome⁽⁷⁵⁾. HPD-associated genes will be visualized in pathway maps to highlight the specific metabolic shifts in the microbiome at the DNA level that occur on a HPD.

Expected results/potential pitfalls: We predict that a HPD will reduce the abundance of genes in phosphotransferase pathways involved in bacterial carbohydrate metabolism, which are elevated in obese humans⁽²⁴⁾. Our estimated final sample size of 80 subjects per group would be much larger than existing metagenomics studies of obese patients which have used 6-7 subjects per group at lower sequence depths (3 GB per sample in the most recent study)^(24,26). We anticipate that the magnitude of effect of a high protein diet will be less than that in those comparisons (obese vs. lean, gastric surgery vs. non-surgically managed) but that the 10 fold larger sample size will provide sufficient power to detect metagenomic shifts.

C. Aim 3. Identify fecal microbial predictors of response to a high protein diet.

Rationale and hypothesis: The second aim of this proposal focuses on the relationship of the microbiome to clinical endpoints including weight loss, body fat loss, lipids, and

hyperglycemia. We hypothesize that subjects will vary in the responsiveness of their microbiota to a HPD based on baseline or post-dietary intervention levels of microbes such as *Akkermansia muciniphila* that respond to the HPD. The impact of these microbial changes on diet-induced weight gain will be assessed in humanized gnotobiotic mice.

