Study design: This is a randomized study using the same subjects described in Aim 1. Nutritional assessment, physical examination, bioelectrical impedance, laboratories will be performed at baseline, and weeks 2, 4, 6, 8, 12 and 16. Stool samples will be collected on day 3, 7, 14, 17, 21, 28, 42, 56, 84 and 112.

Study timeline: Data collection will be completed at week 16. The stool samples collected during the study period will be used for 16S rRNA sequencing, shotgun metagenomics, and data analysis.

Bioinformatics protocol: Patient characteristics (physical measurements, lean body mass, laboratories, demographic traits) at baseline will be compared using a 2-sided t-test (for numerical variables) or chi-square test (for categorical variables) to evaluate the randomization. 3DFR and FFQ performed at each timepoint will be used to assess the predicted protein content of the patient's diet compared to baseline to evaluate the success of the dietary intervention. Clinical response endpoints significantly associated with HPD in Aim 1 will then be correlated with the abundance of microbes found to be enriched or depleted on a HPD in Aim 2.1. These endpoints will be fitted to multivariate models to adjust for baseline clinical covariates including BMI, age, sex, and smoking status. Spearman correlations will then be calculated for all combinations of residuals for the clinical endpoints and for microbial abundance (using DESeq2 fitted multivariate models from Aim 2.1 to adjust for covariates). Separate correlation analyses will be performed at baseline and each of the time points during treatment.

Microbes that are independently associated with clinical response to a HPD will then be used to create random forests classifiers to predict response. Subjects in the HPD group will be identified as responders if they had a decrease in any of the clinical endpoints that exceeded the predictions of the multivariate model for the NPD group. The sensitivity and specificity of the classifiers will be estimated using 10-fold cross-validation. Classifiers constructed from baseline microbial abundance and microbial data at each time point will be compared to determine the earliest time point when accurate predictions of response are possible.

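### If HDL cholesterol qualifies as an Aim 3 endpoint, the responder rule scores it in the wrong direction, because only a decrease counts as response.

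*Combined protocol and SAP*

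**What the plan says.** The responder rule is in section 4.C (Aim 3, Bioinformatics protocol): "Subjects in the HPD group will be identified as responders if they had a decrease in any of the clinical endpoints". The fall must also be larger than a model fitted to the standard protein group would lead one to expect. The plan sets no favourable direction for individual endpoints and exempts none.

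The Aim 3 rationale gives the candidate endpoints as "clinical endpoints including weight loss, body fat loss, lipids, and" hyperglycemia. The list is open-ended and does not say which lipid fractions count. In Aim 1, the Laboratory Studies section heads its lipid panel "Lipids — Cholesterol, High Density Lipoprotein (HDL) Cholesterol, Triglycerides", and the Study Visits list has HDL among the fasting labs. The Secondary Endpoints paragraph includes "laboratory and biochemical variables (e.g., insulin, lipid levels, HbA1c" among the efficacy variables, without naming HDL.

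The Bioinformatics protocol also sets an entry condition: "Clinical response endpoints significantly associated with HPD in Aim 1 will then be correlated with the abundance of microbes" that respond to the diet in Aim 2.1. The Aim 1 secondary tests are two-sided at 0.05.

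**The concern.** For weight, fat mass, total and LDL cholesterol, triglycerides and glucose, a decrease is the wanted change and the rule has the right sign. For HDL the wanted change is an increase. If HDL is in the set, the rule as written credits a fall and ignores a rise. Because any one endpoint suffices, a subject with no favourable change at all can become a responder through a fall in HDL alone.

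The random forest classifiers are trained on this label. Their sensitivity and specificity, the search for the earliest predictive time point and the repeat of the pipeline on the metagenomic data all depend on it. With a reversed endpoint in the set, the classifiers would be predicting a mixture of benefit and harm. A fixed endpoint list or a minimum margin for response would not cure this; the sign would still be wrong.

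**Working it through.** The rule carries no sample size or power figure to reproduce. Two things can be checked: how likely HDL is to enter, and how much the label changes if it does.

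**Inputs.** Preliminary study in non-diabetic subjects (section 3.1.B): HDL change +1.3 mg/dL (high protein) vs +0.5 mg/dL (standard), p=0.62, with 42 and 44 subjects followed up. Section 4.B (Aim 2): about 80 evaluable subjects per group, that is 100 × (1 − 0.20). Two-sided alpha 0.05.

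**Step 1: SD of HDL change.** Assume the p value comes from an unadjusted two-sample t test with 84 df. Then |t| = 0.498, SE = 0.8/0.498 = 1.61, and SD = 1.61/√(1/42 + 1/44) = 7.45 mg/dL. The standardised difference is 0.8/7.45 = 0.11.

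**Step 2: chance of entry at 80 per arm.** SE = 7.45 × √(2/80) = 1.18 mg/dL. The observed difference needed is 1.96 × 1.18 = 2.31 mg/dL, or 0.31 SD. If the true difference is again 0.8, the chance of significance in the upward direction is Φ(0.8/1.18 − 1.96) = Φ(−1.28) = 0.10.

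**Step 3: HDL label if HDL just qualifies.** Take the standard-group prediction as +0.5 mg/dL and changes as normal.
- Upward effect: the high protein mean is 0.5 + 2.31 = 2.81. The share with an actual fall is Φ(−2.81/7.45) = 0.35. These subjects are scored as responders on HDL; those with a rise are not.
- Downward effect: the entry test is two-sided and asks only for association, so harm also qualifies. The mean is 0.5 − 2.31 = −1.81, and the share with a fall is Φ(1.81/7.45) = 0.60.

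**Step 4: share of responders due solely to worse HDL.** Let k be the number of other qualifying endpoints, all of decrease type. Shift every endpoint, HDL included, by 0.31 SD in the favourable direction, take the endpoints as independent, and count any value on the relevant side of the prediction. With q = Φ(−0.31) = 0.378:
- labelled solely through HDL = q^(k+1)
- all labelled = 1 − q^k × (1 − q)
- label differs from the correctly signed one = q^k

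| k | Solely HDL | All labelled | Share of responders | Labels differ |
|---|---|---|---|---|
| 1 | 14.3% | 76.5% | 19% | 38% |
| 2 | 5.4% | 91.1% | 6% | 14% |
| 3 | 2.0% | 96.6% | 2% | 5% |

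If the endpoints, signed for benefit, correlate at 0.3, the share of responders is 23%, 12% and 7%.

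Step 4 counts every HDL value below the prediction (38%), whereas the rule requires an actual decrease (35% in Step 3). The difference is small and makes the table slightly high.

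**The case against.** The strongest reply is that the plan's own entry condition will probably keep HDL out. The only HDL data in the documents are far from significant. The lipid reported as significantly reduced there is triglycerides, for which a decrease is the right direction, so lipids could qualify with no sign error. HDL is never named as an Aim 3 endpoint, and the laboratory text describes assays rather than defining that set. All of this stands. It makes the error unlikely, but it does not correct the rule.

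A reader might infer that HDL will be mis-scored in any event. The documents do not support this, because entry requires a significant Aim 1 association. Nor does a rise in HDL make a subject a non-responder overall, since another endpoint can still qualify.

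A reader might also extend the point to lean mass, since the preliminary study stresses the "potential of increased protein supplementation to result in retention of lean body mass", or to the satiety hormones. Neither is a named Aim 3 clinical endpoint. Aim 3 mentions lean body mass only as a baseline characteristic, and Aim 1 treats the hormone responses as a separate third variable. The most that can be said is that any endpoint for which benefit is an increase would meet the same problem if it were admitted.

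Finally, the Spearman correlations are unaffected: reversing the sign of an endpoint reverses the sign of rho but leaves its size and two-sided p value unchanged.

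**Conclusion.** The point holds conditionally. If HDL, or another endpoint for which benefit is an increase, passes the Aim 1 significance condition, the responder rule scores it backwards, and the two-sided condition does nothing to prevent that. The likelihood is low, about 10% for HDL if the preliminary difference recurs at 80 per arm. The 19% and 38% figures are not general: they belong to a set with one other endpoint and shrink quickly as more decrease-type endpoints qualify.

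This rests on normal changes, a p value from an unadjusted t test, 12-week variability carrying over to 16 weeks, shifts of 0.31 SD, and reading the entry condition as applying to the responder rule as well as to the correlations. The primary endpoint, the sample size and the safety analysis are not touched. It is a minor correction to a secondary predictive analysis.

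**What to change.** In the Aim 3 Bioinformatics protocol, replace the requirement of a decrease in any clinical endpoint with a requirement of a change in the favourable direction in any clinical endpoint. Add a short table giving that direction for each eligible endpoint: decrease for weight, fat mass, total and LDL cholesterol, triglycerides, glucose and HbA1c; increase for HDL. Alternatively, list the lipid fractions that count and leave HDL out. Settle either version before Aim 1 results are known, because those results determine which endpoints enter. The Spearman step can stay as it is. The cost is one sentence and a small table, with no new data or subjects.

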two groups. The data for all time points will then be fitted to a multivariate model under a negative binomial distribution using DESeq2 with diet group, time point, interaction between diet and time point, baseline BMI, age, sex, and smoking status as covariates. This model will be compared to a reduced model that does not include the diet:time point interaction⁽⁷⁰⁾. A likelihood ratio test will be used to identify microbes with differential abundance by diet at time points after baseline. Estimates of significance will be adjusted for multiple hypothesis testing⁽⁷¹⁾. OTUs that are differentially abundant on a HPD will be grouped by hierarchical clustering, which we anticipate will highlight distinct kinetic patterns of microbial change.

Expected results/potential pitfalls: We do not anticipate problems with the collection or transportation of fecal samples to our clinical research unit. We predict that *Akkermansia* will significantly increase on a HPD as was seen in our rodent studies. We further predict that most HPD-responsive microbes will have altered abundance within the first 3 to 7 days as has been observed in other dietary studies^(72,73). We estimate a 20% dropout rate based on our high protein meal replacement study, leaving approximately 80 subjects per group. This compares favorably to published studies reporting dietary effects on the microbiome using sample sizes of 10-15^(72,73,74). We anticipate that a HPD will have a similar magnitude of effect as these previously studied diets and hence we expect to have sufficient numbers to detect compositional differences.

2.2 Identification of metagenes affected by a high protein diet.

Experimental protocol: We will assess the functional consequences of altered microbial composition by sequencing the genes carried by intestinal microbes. Shotgun sequencing of DNA extracted from fecal samples will be performed using the HiSeq 3000 with a target depth of 10 GB data per sample, comparable to the 11.7 GB depth used by the Human Microbiome Project for stool samples⁽⁷⁵⁾. Due to the costs of sequencing at this depth, we will only sequence baseline samples and samples from day 112.

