The above analytic pipeline will then be applied to the shotgun metagenomics data obtained at baseline and day 112. Gene families and/or metabolic pathways that shift in response to a HPD may be more consistent across diverse populations than abundance of specific microbes such as *Akkermansia* which could vary greatly from person to person⁽⁷⁸⁾. The performance of classifiers constructed from metagenes will be compared to those built from microbial abundance to identify the approach that is most predictive for response.

Expected results/potential pitfalls: We predict that a subset of the HPD-associated microbes and metagenes will be associated with response in the HPD. We also expect that baseline and/or post-dietary intervention abundances of microbial features can be used to generate accurate random forests predictors for clinical response. We used similar bioinformatics approaches to identify the inverse correlation of *Akkermansia muciniphila* with body fat in our rodent model and to predict IBD status in families with pediatric inflammatory bowel disease. Accordingly, we do not anticipate problems performing these analyses.

Human Subjects

1. Risk to Subjects

(a) Human Subjects Involvement and Characteristics:

Approximately 198 healthy volunteers age 30 years and older between BMI of 27 to 40 kg/m² will be able to take part in this study. Pregnant women or women likely to become pregnant during the course of the study may not participate in this study. Female subjects must not be

able to conceive by reason of surgery, radiation, 1 year past the onset of menopause, or an approved method of contraception. No vulnerable subjects will be included in the study. (See the detail in the Research Plan, Proposed Work, Aim 1, Sections of Recruitment, Procedures, and Statistical Analysis)

(b) **Sources of Materials:** See the detail in the Research Plan, Proposed Work, Aim 1, Section of Procedures.

(c) **Potential Risks:**

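### Aim 3 treats classifiers built from stool up to day 112 as predicting response, so its later classifiers can report change that has already happened as prediction

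*Combined protocol and SAP*

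**What the plan says.** All places are in the combined protocol and SAP, section 4, WORK PROPOSED.

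- **Sampling (Aims 1, 2 and 3):** "Stool samples will be collected on day 3, 7, 14, 17, 21, 28, 42, 56, 84 and 112".
- **Feature selection (Aim 3, Bioinformatics protocol):** microbes are correlated with clinical endpoints, and "Separate correlation analyses will be performed at baseline and each of the time points during treatment". Those independently associated with response go into the classifiers. The stated adjustment is for baseline covariates: BMI, age, sex and smoking.
- **Responder definition (same place):** "Subjects in the HPD group will be identified as responders if they had a decrease in any of the clinical endpoints that exceeded the predictions" from the control-group model. No assessment day is given.
- **Classifier times (same place):** "Classifiers constructed from baseline microbial abundance and microbial data at each time point will be compared to determine the earliest time point when accurate predictions" can be made.
- **Metagenes:** Aim 2.2 limits shotgun sequencing on grounds of cost: "we will only sequence baseline samples and samples from day 112". Aim 3 continues: "The above analytic pipeline will then be applied to the shotgun metagenomics data obtained at baseline and day 112". The metagene and 16S classifiers are then compared to "identify the approach that is most predictive for response".
- **Primary endpoint (Aim 1, Statistical Analysis):** "the primary endpoint is change in body weight, which is calculated as the difference between Day 1 (baseline) and 16 weeks".

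The plan nowhere requires a sample to precede the outcome. It counts no outcome from the sampling day onward, makes no adjustment for change to date, and does not mark late classifiers as association.

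**The concern.** A predictor has to be known before the thing it predicts. Stool taken at the visit where response is measured cannot meet that condition. Stool taken late in treatment meets it only for the part of the response still to come.

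Weight loss may itself alter stool. The plan's own rationale for Aim 2 cites a phylum ratio that fell in people who lost weight on either of two different diets. A microbe that merely follows weight loss would look like a better and better predictor as the trial goes on.

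Two Aim 3 conclusions are exposed: the earliest day on which response can be predicted, and whether 16S or metagene data predict better. The second is the more exposed, because the only post-baseline metagene sample is the day-112 one.

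**Working it through.** **1. Calendar.** 16 weeks × 7 = day 112, the last stool day. (Counting baseline as day 0 or Day 1 moves this by one day and changes nothing.) Visits at weeks 2, 4, 6, 8, 12 and 16 fall on days 14, 28, 42, 56, 84 and 112, all of them stool days. Stool days 3, 7, 17 and 21 have no clinic visit.

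**2. Which response day?** Week 16 is borrowed from the Aim 1 primary endpoint. If response were instead judged at each visit, every visit-matched on-treatment classifier would be concurrent with its outcome. Either way the day must be stated.

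**3. Sample behind Aim 3.** Aim 3 gives no sample size or accuracy target of its own. Aim 2.1 expects about 80 per group after 20% dropout: 100 × (1 − 0.20) = 80, which reproduces.

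**4. Overlap, for weight only.** Assume loss accrues evenly, in independent increments of equal variance, from day s to day 112. The share accrued by day t is (t − s)/(112 − s), and the correlation of loss to date with final loss is the square root of that share. Calorie restriction starts at week 2, hence s = 14. Macronutrient change starts at the initial visit, so s = 0 is shown as the other end of the range.

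| Day | Share, s = 14 | Correlation | Share, s = 0 | Correlation |
|---|---|---|---|---|
| 14 | 0/98 = 0% | 0 | 14/112 = 12.5% | 0.35 |
| 17 | 3/98 = 3% | 0.17 | 17/112 = 15% | 0.39 |
| 21 | 7/98 = 7% | 0.27 | 21/112 = 19% | 0.43 |
| 28 | 14/98 = 14% | 0.38 | 28/112 = 25% | 0.50 |
| 42 | 28/98 = 29% | 0.53 | 42/112 = 37.5% | 0.61 |
| 56 | 42/98 = 43% | 0.65 | 56/112 = 50% | 0.71 |
| 84 | 70/98 = 71% | 0.85 | 84/112 = 75% | 0.87 |
| 112 | 100% | 1.00 | 100% | 1.00 |

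**5. What this can do to accuracy.** A simulation took 80 high-protein subjects (3,000 replicates), independent weight increments, and response defined as above-median week-16 loss. It used one microbe with no prognostic information that only follows weight already lost. Its correlation with loss at day 112 was assumed to be 0.3, 0.5 or 0.7; none of these values is in the documents. AUC for week-16 response, in that order:

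| Day | s = 14 | s = 0 |
|---|---|---|
| Baseline | 0.50 / 0.50 / 0.50 | 0.50 / 0.50 / 0.50 |
| 14 | 0.50 / 0.50 / 0.50 | 0.52 / 0.53 / 0.55 |
| 28 | 0.52 / 0.54 / 0.56 | 0.53 / 0.56 / 0.60 |
| 56 | 0.56 / 0.61 / 0.66 | 0.57 / 0.62 / 0.68 |
| 84 | 0.60 / 0.67 / 0.75 | 0.60 / 0.68 / 0.76 |
| 112 | 0.64 / 0.73 / 0.83 | 0.64 / 0.73 / 0.83 |

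The baseline AUC correctly shows nothing and the day-14 value is at most 0.55. The late values look useful although the microbe carries no information about the future. The planned 10-fold cross-validation guards against overfitting, not against this.

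**The case against.** The other side has a good deal to say.

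- The plan keeps a separate baseline classifier and asks for the earliest usable day. Six of the ten listed stool days fall by day 28, and Aim 2.1 expects most microbial change within 3 to 7 days. **This stands.** A reader might infer that every on-treatment classifier is invalid and that prediction must rest on baseline stool alone. The documents do not support that: samples up to day 14 come before or at the start of calorie restriction, and post-intervention levels are part of the stated Aim 3 hypothesis.
- Response is not raw weight loss. It is a decrease in any endpoint beyond the control-group prediction, for endpoints associated with the high protein diet in Aim 1. The preliminary study of the same two protein levels (section 3.1.B) found no weight difference (−11.1 vs −11.9 lbs, p = 0.80), so weight might not qualify at all. **This stands.** A reader might take the 0.85 at day 84 to mean that a scale would do the classifier's job; it shows only how overlap grows for one endpoint under assumed increments.
- 16S and shotgun data both exist at baseline, so a like-for-like comparison is possible under the current text. **True**, but the text does not confine the comparison to baseline or rule out ranking on day 112.
- Aim 3 carries no power claim and the trial is sized on Aim 1. **This stands**, and it limits the severity.

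None of this answers the central point: day 112 is week 16, and nothing in the plan separates association at that visit from prediction.

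**Conclusion.** The concern holds in a limited form. If response is assessed at week 16, the day-112 16S and metagene classifiers are concurrent with the outcome. Samples from about day 28 to day 84 partly overlap change already made, so their accuracy can rise with sampling day without predictive content. Baseline and days 3 to 14 are not materially affected.

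The week-16 date is inferred from the primary endpoint. The size rests on assumed accrual: for weight, a correlation between change to date and final change of 0.38 to 0.50 at day 28 and 0.85 to 0.87 at day 84, across the two start days.

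A reader might infer that both Aim 3 conclusions are bound to be unsound. That does not follow. Accuracy found at baseline or in the first two weeks could be real, and a baseline 16S-versus-metagene comparison would be sound. The fault is that the plan as written does not tell these cases from the others.

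The primary weight analysis is untouched. Should-fix.

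**What to change.** 1. State that response for Aim 3 is assessed at week 16.
2. Label the day-112 16S and metagene classifiers as association, and make the 16S-versus-metagene prediction comparison on baseline stool.
3. Keep baseline and early on-treatment stool as prediction analyses. For samples at clinic visits (days 14, 28, 42, 56 and 84), define the outcome as endpoint change from that visit to week 16, or report the accuracy added over baseline covariates plus endpoint change to date. For days 17 and 21 use the nearest preceding visit (day 14). For days 3 and 7 use baseline covariates alone.

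One dependency: the listed stool days begin at day 3, while the Aim 1 Study Visits list includes stool at week 0 and Aim 2.2 relies on baseline samples. These should be reconciled, since steps 2 and 3 need the baseline sample.

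The cost is SAP wording and extra model fits on data already planned, with no added visits or sequencing. If the from-visit outcome is chosen, the control-group model that defines responders must be refitted for each visit. The downside is that later landmarks have a shorter outcome window and less signal.
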